## 7.2 Randomization

Participants will be randomized to either CLEAR therapy or placebo at a ratio of 1 to 1 stratifying by site and use of prednisone  $\geq 10$  mg or not and using a permuted-block randomization algorithm with random block sizes. Treatment assignments of the study will be made using separate randomization schedules for each of the three participating sites. The randomization schedule will be prepared by the DCC prior to initiation of patient recruitment. Randomization schedules will be generated by a statistician who is not involved with the conduct of the clinical trial. All randomization schedules will be generated using R, will remain confidential and known only by the site pharmacists until the database is locked and randomization assignments no longer must be blinded. Randomization marks the patient's official entry into the Study. Once a participant has been started on the assigned study treatment, efforts will be made to conduct all evaluations irrespective of whether the participants complete the study treatment regimen or not, or how well the participants complies with the study treatment regimen. These efforts should continue until termination of the study. Data collections will continue even if medication must be stopped.

For the intention to treat analysis, participants will be considered treated when the first study drug is taken, regardless of the amount of study drug they receive. Participants discontinued from receipt of

study drug for any reason, will continue to follow all other protocol requirements for the entire study period to the extent that the informed consent is still active.

### 7.3 Sample Size Justification

Sample size is calculated for primary endpoint; change from baseline of FVC percent predicted. Using data from 34 participants treated with Bosentan to treat pulmonary hypertension, we obtained the SD of 7.7 for the primary endpoint. We need a sample size of 51 completed participants per arm to have 90% power to detect a 5% difference (5% in CLEAR vs. 0% in placebo) in change of FVC percent predicted from baseline. To factor in a 20% dropout rate, we plan to enroll 64 subjects per arm. This brings the sample size to 128 participants. In the Phase I trial, we experienced a higher drop rate 30%, but review of the clinical data demonstrates that patients with advanced disease accounted for the majority of the study withdrawals. The Phase II trial will allow patients to drop one study drug, and will include a research nurse coordinator to encourage study participation. We anticipate that we will have not have as high a study withdrawal rate.

### 7.4 Interim Monitoring

The DSMB will receive a report of adverse events (blinded by arm) after 15 participants have completed study treatment to review. This review will be conducted by the chair of the DSMB, who will recommend either that the study continue or that there be a review of the first 15 participant's data by the DSMB committee. An interim safety analysis will also be performed after 50 participants complete study drug treatment. This interim analysis will be presented to the DSMB by the PI and the study statistician or his/her designee. The results will be blinded and presented on a coded study arm basis (i.e. A and B arm) unless the DSMB votes to receive unblinded data. The interim analysis will focus on the safety profile of the study treatments. These analyses will be conducted based on the methods specified in the Data Analysis Plan for the safety endpoints. Since the interim analysis is not designed to draw formal inference on these safety endpoints, the magnitude of the between-treatment differences and the p-values will be provided solely to help the DSMB to evaluate the safety profile. Although efficacy data will also be presented, no early stopping of the trial based on the efficacy endpoints is planned for this Phase II study, because it is unlikely that an efficacy study of less than 128 subjects will have credibility with the scientific community. The DSMB is further described in Section Data Safety Monitoring Board Charter and Plan.

### 7.5 Futility

There will be no formal futility analysis for efficacy.

### 7.6 Data Safety Monitoring Board Overview

#### 7.6.1 Data and Safety Monitoring Board (DSMB)

The committee will consist of three members, in addition to the study statistician. DSMB will be comprised of adult specialists with extensive clinical experience in sarcoidosis/ interstitial lung disease and clinical trial research experience. Members will be independent and have no conflict of interests related to the study or drug of study. The study statistician will be an ex-officio (non-voting) member of the DSMB.

#### 7.6.2 DSMB role and responsibilities

The DSMB role and responsibilities will involve conducting interim monitoring of accumulating data from research activities to assure the continuing safety of human participants, relevance of the study question, appropriateness of the study, and integrity of the accumulating data. The committee will also identify protocol violations that suggest clarification of changes to protocol are needed; identify unexpectedly high dropout rates that threaten the trial's ability to produce credible results; ensure the

credibility of the study; ensure the validity of study results as well as to protect the safety of trial participants.

### **7.6.3 Confidential Reports**

All reports of efficacy and futility monitoring will be blinded with regard to treatment assignment and will be reviewed in a closed session of the DSMB meeting. The DSMB will discuss unblinded results in the closed session. Safety data will not be blinded to the DSMB. Unexpected adverse events and unanticipated events will be reported and reviewed on an ongoing basis by the DSMB chair who may request input from other DSMB members if thought necessary.

### **7.6.4 Scheduled meetings**

The first meeting of the DSMB will occur at study initiation, with the purpose of approving the statistical monitoring plan. The second DSMB meeting will occur when the statistical report on data for 50 enrolled participants is available for review. The statistical center will be monitoring the data continuously and may call a DSMB meeting at any time after 25 participants have been accrued and when warranted by the data, as described above. The calendar timing of these meetings will be participant to the overall rate of recruitment. The open portion of DSMB reports will be made available to participating sites. Discussions and actions items from the closed portion of the meeting will remain confidential. In the event of slow patient recruitment, the DSMB will meet by teleconferencing every 6 months for year one, then annually to review the safety analyses conducted by the Data Coordinating Center (DCC) and determine whether the study should be (a) allowed to continue, (b) modified, or (c) discontinued.

All severe adverse events (SAEs) will be reported to the DSMB as well as to all the IRBs involved in the study. The DSMB may choose at any time to have an additional DSMB meeting to determine if a change in protocol or informed consent is needed based on SEAs. Also, the DSMB will comment on the SAEs in their yearly report; the committee will also supervise the preparation of the interim confidential reports.

## **8. Data Collection and Site Monitoring**

### **8.1 Data Collection**

Investigators or research coordinators will collect data and enter it directly into the web-based data entry system managed by the Clinical Coordinating Center or record on paper data forms for later entry into REDCap, a web-based data entry system.

A screening log will be maintained for those potential participants who are contacted for screening in this study. The log will include the reason if the potential participant was not enrolled. Data entry by coordinating center personnel into REDCap of screening log data will not include private information. Clinical sites will maintain the screening log in their research files.

#### **8.1.1 Data Collection Training**

Quality data collection and appropriate study conduct will require careful attention to the training of research personnel at the Clinical Core Coordinating Center and participating sites. Training sessions for the Study Coordinators and key personnel will be held prior to the initiation of patient recruitment. The protocol, forms, and other materials will be distributed to the appropriate personnel. Each center's personnel will be trained centrally in the study requirements, standardization measurement of height, weight, phlebotomy, and requirements for laboratory specimen collection including counseling on adherence, and in eliciting of information from study participants in a reproducible manner.

Training will be performed by Clinical Coordinating Center personnel. Inclusion and exclusion criteria, data to be collected and the procedures to be conducted at each visit will be reviewed in detail. Data collection forms and the nature of the required information will also be discussed in detail. Entering data

remotely, responding to data queries and general information about obtaining research quality data will also be covered during the training session.

## 8.2 Site Monitoring

Sites will be monitored on a regular basis by the Clinical Coordinating Center (CCC), to ensure that all regulatory requirements are met and to monitor the quality of the data collected. Records of Institutional Review Board approvals will be faxed or sent electronically to the CCC. REDCap database automated range checking may be utilized to alert data entry personnel when data out of range is entered. Data quality assurance checks will be performed to assure the data are as accurate as possible prior to locking the database. If erroneous or inappropriately missing data are noted from any one site, the CCC will develop a corrective action plan for the site(s) involved.

## 9. Risk Assessment

### 9.1 Risks of Antimycobacterial Therapy (Levaquin, Ethambutol, Azithromycin, and Rifamycin)

Potential risks of study drugs are described below. All of the prescribed medications are well tolerated and adverse events are reports in less than 0.7% of patients. We are using the current FDA recommended doses.

#### 9.1.1 Levaquin:

**Common ( $\geq 3\%$ ):** in US clinical trials were nausea, headache, diarrhea, insomnia, constipation, and dizziness. An increased chance of problems with the joints and tissues around the joints has been observed in pediatric patients receiving levaquin and the safety in pediatric patients treated for more than 14 days has not been studied.

**Uncommon ( $< 3\%$ ):** tear of a tendon, increased risk of tendinitis, tendon rupture in all ages allergic reaction, liver function problems, nervous system effects (tremors, anxiety, lightheadedness, depression, insomnia (trouble sleeping), diarrhea, nerve problems such as numbness or tingling in your hands/feet, abnormal heart rhythms, changes in your blood sugar levels, sensitivity to light, nausea, headache, constipation and dizziness.

**Rare ( $< 1\%$ ):** prolonged the QT interval or induced Torsades de Pointes (it should not be used in patients with known prolonged QT intervals or a family history of such), increased risk of tendinitis and tendon rupture in all ages. This risk is further increased in older patients usually over 60 years of age, in patients taking corticosteroid drugs, and in patients with kidney, heart, or lung transplants [21], shortness of breath, abdominal pain, vomiting, upset stomach, rash, itching, swelling in your arms or legs, chest pain.

#### 9.1.2 Ethambutol:

**Common ( $> 10\%$ ):** Appetite loss; disorientation; dizziness; general body discomfort; headache; nausea, stomach upset, vomiting

**Uncommon ( $< 3\%$ ):** Severe allergic reactions (rash; hives; itching; difficulty breathing; tightness in the chest; swelling of the mouth, face, lips, or tongue); chest pain or tightness; confusion; dark urine; easy bruising or bleeding; fever, chills, or sore throat; hallucinations; joint pain, swelling, or severe tenderness; lower back pain; numbness or tingling of the hands, legs, or feet; severe stomach pain; swollen glands in the neck or armpit; vision loss or other vision changes; yellowing of the skin or eyes.

**Rare ( $< 1\%$ ):** decreases in visual acuity, including irreversible blindness, which appear to be due to optic neuritis. Optic neuropathy including optic neuritis or retrobulbar neuritis occurring in association with ethambutol therapy may be characterized by one or more of the following events: decreased visual acuity, scotoma, color blindness, and/or visual defect. These events have also been reported in the absence of a diagnosis of optic or retrobulbar neuritis. Optic neuropathy has not been reported in participants on therapy  $< 90$  days

**9.1.3 Azithromycin:**

**Common (>10%):** Diarrhea; headache; loose stools; nausea; stomach pain; upset stomach; vomiting.

**Uncommon (<3%):** Severe allergic reactions (rash; hives; itching; difficulty breathing; tightness in the chest; swelling of the mouth, face, lips, or tongue; unusual hoarseness); bloody stools; changes in hearing or hearing loss; chest pain; eye or vision problems; irregular heartbeat; muscle weakness; pounding in the chest; red, swollen, blistered, or peeling skin; ringing in the ears; seizure; severe diarrhea; stomach cramps/pain; trouble speaking or swallowing; yellowing of the skin or eyes; decreased hemoglobin, hematocrit, lymphocytes, neutrophils and blood glucose; elevated serum creatinine phosphokinase, potassium, ALT, GGT, AST, BUN, creatinine, blood glucose, platelet count, lymphocytes, neutrophils and eosinophils;

**Rare (<1%):** leukopenia, neutropenia, decreased sodium, potassium, platelet count, elevated monocytes, basophils, bicarbonate, serum alkaline phosphatase, bilirubin, LDH and phosphate. The majority of participants with elevated serum creatinine also had abnormal values at baseline.

**9.1.4 Rifamycins (rifampin or rifabutin):**

**Common (>10%):** tired feeling; or red or orange colored urine, stools, tears, sweat, or saliva

**Uncommon (<3%):** Allergic reaction (hives; difficulty breathing; swelling of your face, lips, tongue, or throat), fever, chills, body aches, flu symptoms, joint pain or swelling, easy bruising or bleeding, weakness, urinating less than usual or not at all, nausea, stomach pain, loss of appetite, itching, dark urine, clay-colored stools, jaundice (yellowing of the skin or eyes), neutropenia (a low white blood cell count that may make it more likely for you to get infections).

**Rare (<1%):** Rifampin has been shown to produce liver dysfunction. Fatalities associated with jaundice have occurred in patients with liver disease and in patients taking rifampin with other hepatotoxic agents. Patients with impaired liver function should be given rifampin only in cases of necessity and then with caution and under strict medical supervision. In these patients, careful monitoring of liver function, especially SGPT/ALT and SGOT/AST should be carried out prior to therapy and then every 2 to 4 weeks during therapy. If signs of hepatocellular damage occur, rifampin should be withdrawn. Hematological side effects have included thrombocytopenia, leukopenia, hemolytic anemia, and decreased hemoglobin, in less than 1% of patients. Hyperbilirubinemia and hepatitis have been reported in up to 3% of patients. Approximately 50% of hepatotoxicity has been observed during the first month of therapy.

**9.2 Risks of Phlebotomy**

All patients will have blood drawn for research purposes. Risks of drawing blood are uncommon and include bleeding and bruising, and a rare risk of fainting or infection.

**9.3 Risks of Bronchoscopy**

Bronchoscopy is very safe, but no procedure is entirely free of potential risk. The chance of serious complications is reported to be less than 0.05% (5 in 10,000). Local discomfort (coughing, gagging, and soreness of your nose and throat) are frequently unavoidable but can be greatly diminished with medication. Nosebleed, wheezing (about 1% chance), a decrease in blood oxygen requiring that requires wearing an oxygen mask, low grade fever (less than a 5% chance), lung infection (pneumonia) in less than 0.1%, and coughing up small flecks of blood for 24 hours after the procedure (as a result of minor trauma to the bronchial lining) may occur (less than a 5% chance). Vocal Cord spasm can result in hoarseness and bronchial spasm can cause wheezing or shortness of breath. Mild bronchitis is common after bronchoscopy. Occasionally, antibiotics and/or a short course of corticosteroids are required if patients are significantly symptomatic. More serious complications such as major bleeding, lung collapse,

vocalcord and bronchial spasm, and heart problems have been reported but are very rare. It is not expected that patients will experience all of these side effects.

#### **9.4 Minimization of Risks**

Federal regulations at 45 CFR 46.111(a) (1) requires that risks to subjects are minimized by using procedures which are consistent with sound research design. There are several elements of study design in the present protocol that meets this human subject protection requirement.

Several of the exclusion criteria prohibit participation of patients who might be at increased risk from the effects of antimycobacterial therapy. For example, patients who have intolerances or allergies to any drug in this regimen, pregnancy, and who are taking medications that may unfavorably interact with a drug in the regimen are excluded. Also, we will monitor for adverse effects to liver and muscle by monitoring ALT. We will stop study medications if the ALT rises to more than 10 times ULN.

#### **9.5 Potential Benefits**

There have been no peer-reviewed studies assessing the benefits of antibiotic therapy in sarcoidosis pathogenesis. The potential benefit of this proposed study is that it may alter the natural history of this disease for which there is no cure. It may result in less immunosuppressant therapy being used for sarcoidosis patients, and potentially complete resolution of their disease.

#### **9.6 Risks versus Benefits**

The risks of the proposed regimen are minimal, especially with the rigorous exclusion criteria. The benefits include short term therapy that is much less expensive, compared to immunosuppressives which are more costly and carry greater longer term toxicities. Phase I analysis supports that this regimen may alter the natural history of the disease in patients sarcoidosis, and obviate the necessity of immunosuppressant therapy.

## **10. Human Subjects Protection**

### **10.1 Institutional Review Board Involvement**

The protocol and the informed consent documents to be used in this study will be submitted to the investigator's local IRB for approval. Written documentation of approval of the protocol and the informed consent documents must be provided to CCC before starting the study.

The investigator will promptly report to their local IRB all changes in the research activity and all unanticipated problems involving risks to human subjects or others, and will not make changes in the research without prior IRB approval, except where necessary to eliminate apparent immediate hazards to human subjects.

### **10.2 Equitable Selection of Participants**

The exclusion criteria for this study neither unjustly exclude classes of individuals from participation in the research nor unjustly include classes of individuals from participation in the research.

### **10.3 Informed Consent**

The investigator is responsible for ensuring that the patient or patient's legally authorized representative understands the risks and benefits of participating in the study, and answering any questions the patient may have throughout the study and sharing any new information in a timely manner that may be relevant to the patient's willingness to continue his or her participation in the trial. Prior to a participant's enrollment in the study, the investigator will ensure that the purpose of the study is explained to the patient and that written consent is obtained.

All study participants will be informed of the objectives of the study and the potential risks. The informed consent document will be used to explain the risks and benefits of study participation to the patient in simple terms before the patient is entered into the study, and to document that the patient is satisfied with his or her understanding of the risks and benefits of participating in the study and desires to participate in the study. The investigator is responsible for ensuring that informed consent is given by each patient or legal representative. This includes obtaining the appropriate signatures and dates on the informed consent document prior to the performance of any protocol procedures and prior to the administration of study agent.

The patient will receive a copy of his/her signed consent form. The investigator will retain a copy of the signed consent forms. The investigator will follow local guidelines for seeking informed consent from persons who may need additional protections, such as those who do not read.

#### **10.4 Sequence of Consent Procedures**

It is recognized that the Site-specific Center and participating site IRB have official responsibility for determining informed consent procedures. Prototype informed consent forms have been developed for this study. A FDA-approved IND number is not indicated for this trial.

#### **10.3 Confidentiality**

At the beginning of the study, each patient will be assigned a unique identification number and a study code. In any individual tabulation, participants will be identified only by number. The medical records of participants in CLEAR Trial will be confidential. All procedures will be in compliance with HIPAA regulations.

To maintain confidentiality, evaluation forms and reports entered into the study database will be identified only by the participant's coded number. The coded number will be generated at random by a computer, and only the study investigators will have access identity of the participant corresponding to the codes. All electronic records will be kept in a locked, password protected computer. All computer entry and networking programs will be done with coded numbers only. All source documents containing the participant's identifiable information will be maintained in a locked cabinet inside a locked office. Clinical information will not be released without the written permission of the patient, except as necessary for monitoring by the Institutional Review Board, National Heart, Lung, and Blood Institute, the Federal Drug Administration or other authorized Federal Agencies, and the Clinical Coordinating Center.

Data will be entered into REDCap, an electronic web-based database, for storage and only research staff with appropriate permissions will be allowed to access the database. Data will be automatically sequestered by site so that individuals at any institution may see their own site's data, but not data collected at other sites. Primary study coordinators will have no access to case report form data views, but will instead have rights to use a single export module designed to enable export of all site data. No identifiable information, with the exception of dates will be collected. To allow for remote monitoring, source documents containing patient identifiers may be uploaded into REDCap, a HIPAA secure, password protected web-based database.

## **11. Adverse Event Reporting**

Investigators will determine if any clinical adverse experiences occur during the period from enrollment through study month 6 or hospital discharge or death, whichever occurs first. The investigator will evaluate any changes in laboratory values and physical signs and will determine if the change is clinically important and different from what is expected in the course of treatment of patients with sarcoidosis. If clinically important and unexpected adverse experiences occur, they will be recorded on the adverse event case report form.

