### 3.2 Secondary Endpoints:

- Change in FEV1
- Radiographic improvement in sarcoidosis lung disease by frontal chest x-ray. Local investigators will score chest x-rays. This analysis correlates roentgenographic findings with physiologic parameters.
- Change in 6 minute walk distance, oxygen saturation and level of dyspnea.
- Change in the Saint George's Respiratory Questionnaire (SGRQ; King's Sarcoidosis Questionnaire (KSQ) for the assessment of health status; The Fatigue Assessment Scale (FAS).
- Necessity of escalating immunosuppressive therapy secondary to continued clinical deterioration, after study enrollment.
- Safety profile of regimen as evidenced by adverse events and abnormal lab values, tolerability and toxicity of the treatment regimen including comparison of reported adverse events and abnormal laboratory values compared to placebo.
- Increase in T cell biologic function through normalization of p56Lck and IL-2 expression.
- Decrease in peripheral and pulmonary T cell responses against ESAT-6 at 16 weeks compared to baseline.

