#### **5.5 Assessment of Drug Adherence:**

Participants should be asked to return the pill bottles and medication diary at each visit. Pill counts should be conducted at each visit and reconciled with quantities dispensed, and a review of medication diary to assess adherence to prescribed regimen and the onset of new symptoms should be conducted. If a participant misses a dose, they will receive guidance on making up missed dose

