## 6.8 Assessments for Data Collection

Data will be collected to assess the following endpoints:

- FVC percent predicted, FVC, FEV1 at baseline, week 4, week 8, and week 16
- Radiographic assessment of sarcoidosis lung disease using the Muer scoring system at baseline, week 4, week 8, and week 16.
- Change in 6 minute walk distance and oxygen saturation from baseline to 16 weeks.
- Change in questionnaires from baseline to 16 weeks.
- Decrease in peripheral and pulmonary T cell response to mycobacterial antigens between baseline and 16 weeks, as well as T cell function assays.
- Adverse events, assessments and laboratory results for safety analysis.
- Standard of care therapies.

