#### 7.1.4 Analysis of Secondary Endpoints

For continuous secondary endpoints, statistical analyses will be conducted using the same methods as described for the primary endpoint. For binary endpoints such as >10% improvement on FVC, the Pearson chi-square test or Fisher's exact test will be used to assess them between the two arms. If imbalance on certain important covariates which might impact these binary endpoints is observed between the treatment arms, logistic regression to control for these covariates may be conducted. The safety endpoint such as death, AE, SAE, drug-related AE, drug-related SAE, abnormal lab values, tolerability and toxicity of the treatment regimen, will be summarized (count and percent) by treatment arms and for the entire study sample. Between CLEAR and placebo comparison on these endpoints will be made using the Pearson chi-square test or Fisher's exact test.

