### 11.1 Reportable Adverse Event

For this trial, a **reportable adverse event** is defined as:

- Any clinically important untoward medical occurrence in a patient receiving study drug or undergoing study procedures which is different from what is expected in the clinical course of a sarcoidosis patient or,
- Any clinically important, untoward medical occurrence that is thought to be associated with the study drug or procedures, regardless of the “expectedness” of the event for the course of a sarcoidosis patient.

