### 11.2 Expected events for sarcoidosis

Expected events for sarcoidosis are untoward clinical occurrences that are perceived by the investigator to occur with reasonable frequency in the day to day care of sarcoidosis patients. Examples of adverse events that are expected in the course of this study include dyspnea upon exertion, arthralgias, myalgias, etc. Such events, which are often the focus of prevention efforts as part of sarcoidosis care, will not be considered reportable adverse events unless the event is considered by the investigator to be associated with the study drug or procedures, or unexpectedly severe or frequent for an individual sarcoidosis patient. All SAEs or clinically significant laboratory abnormalities which, in the opinion of the investigator, may be due to study drug or study procedures will be monitored until complete resolution, until the condition stabilizes, or until the participant is lost to follow-up.

Investigators will report all events that are **serious AND unexpected AND study-related, as defined in Manual of Operations and Procedures**, to the Clinical Coordinating Center by phone, fax or email within 24 hours of becoming aware of event. The local Institutional Review Board must also be notified in a timely manner. The investigator will then submit a detailed written report to the Clinical Coordinating Center and the Institutional Review Board no later than 5 calendar days after the investigator discovers the event.

The Clinical Coordinating Center will report all serious, unexpected, and study-related adverse events to the DSMB, by email, or telephone, within 7 calendar days of the CCC being notified of the event. A written report will be sent to the DSMB within 15 calendar days, and these reports will be sent to investigators for submission to their respective Institutional Review Boards. The DSMB will also review all adverse events during scheduled interim analyses. The Clinical Coordinating Center will distribute the written summary of the DSMB’s periodic review of adverse events to investigators for submission to their respective Institutional Review Boards in accordance with reporting guidelines.

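### Section 11 can end adverse event collection at hospital discharge, against the week 24 schedule, and can be read to leave milder, unattributed joint and muscle symptoms unrecorded that Section 6 collects.

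*Combined protocol and SAP*

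**What the plan says.** **The window.** Section 11 has investigators determine AEs from enrollment until the earliest of study month 6, hospital discharge or death. Section 6.7 and Appendix A assess AEs at week 24. Section 5.1 keeps participants who stop study drug under all other protocol requirements for 180 days. Sections 7.2 and 12.1 continue data collection after drug is stopped.

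**What goes on the form.** Section 11: "If clinically important and unexpected adverse experiences occur, they will be recorded on the adverse event case report form". Section 11.1 makes two kinds of event reportable: clinically important events that differ from the expected course of sarcoidosis, and "Any clinically important, untoward medical occurrence that is thought to be associated with the study drug or procedures, regardless of the" expectedness of the event. Section 11.2 then says: "Examples of adverse events that are expected in the course of this study include dyspnea upon exertion, arthralgias, myalgias, etc". These are not reportable unless the investigator links them to drug or procedures, or finds them unexpectedly severe or frequent for that patient.

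**What is collected elsewhere.** Sections 6.4 to 6.7 have sites record new signs or symptoms, and AEs, at weeks 4, 8, 16 and 24. Section 5.5 adds a "review of medication diary to assess adherence to prescribed regimen and the onset of new symptoms should be conducted". Section 6.8 lists "Adverse events, assessments and laboratory results for safety analysis". None of these carries the Section 11 filter.

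**What is analysed.** Section 3.2 describes the safety endpoint as "including comparison of reported adverse events and abnormal laboratory values compared to placebo". Section 7.1.4 (Analysis of Secondary Endpoints) lists "The safety endpoint such as death, AE, SAE, drug-related AE, drug-related SAE, abnormal lab values" for summary and testing by arm. Section 11.2 adds: "The DSMB will also review all adverse events during scheduled interim analyses".

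**The concern.** Safety is part of the primary objective (Section 2.1), and AEs are tested between arms. Two features of Section 11 can make the AE data incomplete.

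First, the discharge limit falls on participants who have been in hospital. They are likely to include those with serious events, and a safety analysis can least afford to lose them.

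Second, arthralgia and myalgia are named as expected in the disease, yet joint pain is also a listed reaction to ethambutol (Section 5.2.2) and the rifamycins (Section 5.2.4) and, when extreme, to Levaquin (Section 5.4). For milder joint pain, recording would turn on a blinded investigator deciding whether a symptom expected from both disease and drug belongs to the drug. Sites following Section 6 would record such an event; sites following Section 11 might not.

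**Working it through.** The plan states no AE rate or capture rate, so there is no planned figure to reproduce. The check sets the text side by side and adds simple arithmetic.

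**1. Cost of the discharge limit for one participant.** Inputs: 16 weeks of treatment (Section 5.3) and AE visits at weeks 4, 8, 16 and 24 (Appendix A). For discharge at week w, just after any visit due that week, follow-up lost = (24 − w)/24 and treatment weeks lost = (16 − w)/16.

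| Discharge | Follow-up lost | Treatment weeks lost | AE visits lost |
|---|---|---|---|
| Week 4 | 20/24 = 83% | 12/16 = 75% | 3 of 4 |
| Week 8 | 16/24 = 67% | 8/16 = 50% | 2 of 4 |
| Week 16 | 8/24 = 33% | 0/16 = 0% | 1 of 4 |

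On the 180-day period of Section 5.1 the first two follow-up losses become (180 − 28)/180 = 84% and (180 − 56)/180 = 69%, which changes nothing of substance. The documents give no hospitalisation rate, so the number of participants affected cannot be estimated.

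**2. Does other text restore these events?** Section 7.6.4 sends all SAEs to the DSMB with no discharge limit, but that is a reporting route, and it does not cover non-serious events. Section 11.2 follows SAEs and significant laboratory abnormalities that may be study-related until they resolve or stabilise. That covers existing events, not new ones after discharge.

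**3. One event under each section.** Take new, mild arthralgia at week 8 that the investigator does not attribute to study drug.
- Section 6.5: a new symptom, to be recorded.
- Section 11: expected in sarcoidosis, so outside the class that the section sends to the form.
- Section 11.1: neither unexpected nor attributed, so not reportable.
- Section 11.2: not reportable, since neither exception applies.
- Section 7.1.4: AE is listed separately from drug-related AE, which suggests that unattributed events were meant to be counted.
- Section 3.2: the comparison is of reported events, which could mean the Section 11 set.

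No section settles which record is used.

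**4. Direction of the effect.** Recorded incidence = true incidence × share captured. Assume, for illustration only, true joint-pain incidence of 30% on CLEAR and 10% on placebo.
- Equal capture of 75%, 50% or 25% gives 22.5% v 7.5%, 15% v 5%, or 7.5% v 2.5%. The difference of 20 points falls to 15, 10 or 5.
- If half the participants are at sites that record everything and half at sites with 50% capture, overall capture is 0.5 × 1 + 0.5 × 0.5 = 0.75, again giving 22.5% v 7.5%.
- If only the 10% background is half missed and the 20-point drug excess is fully attributed and recorded, the result is 5% + 20% = 25% v 5%. The difference stays at 20 points.

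Incidence reads low in both arms in every case, but the arm difference may shrink or stay the same. The documents cannot say which.

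**The case against.** The strongest reply is that Section 11 is coherent: Section 11.1 defines a reportable event for this trial, Section 3.2 compares reported events, and Section 6 only schedules when to ask. On that reading the filter is a deliberate choice. It is a possible reading, but Section 3.2 names no form, and Section 7.1.4 lists AEs apart from drug-related AEs. The choice should be stated.

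Several stronger inferences do not hold:
- **That Section 11 bars expected events from the form.** It says which events will be recorded but not that only those may be, and Sections 11.1 and 11.2 speak of reportable events. Exclusion is one reading, and the ambiguity is the defect.
- **That severe joint pain is lost.** Extreme pain would probably meet the severity or attribution exception. The gap is milder, unattributed symptoms.
- **That exertional dyspnea disappears.** The Borg score is taken at screening and at weeks 4, 8, 16 and 24, and level of dyspnea is a secondary endpoint. Dyspnea is partly covered, and laboratory values are compared separately.
- **That blinded attribution is itself a flaw.** Blinding protects the judgement. The difficulty is making recording depend on that judgement.

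The discharge limit may well be stray text, since so much else continues follow-up. That is a reason to delete it, not to leave it in force. Section 11.2 cites a Manual of Operations and Procedures that is not among the documents, but only in connection with serious, unexpected, study-related events.

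**Conclusion.** The concern holds in two parts. The discharge limit contradicts the week 24 AE assessment and the continued follow-up. Applied literally, it removes new AEs after discharge: up to 3 of 4 AE visits and 12 of 16 treatment weeks for a participant discharged at week 4. Only participants hospitalised and discharged during the study are affected, and their number is unknown.

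The recording rule can be read to omit milder, unattributed arthralgia and myalgia that Section 6 collects. The likely result, if sites read it that way, is under-recorded incidence in both arms and differences between sites in what is recorded. A reader might infer that the comparison is biased or loses power in a known direction. The documents do not support that, because they give neither event rates nor capture rates. The primary FVC analysis is not touched. The wording should be corrected because safety is part of the primary objective and the remedy is cheap.

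**What to change.** - **Section 11, window:** remove the reference to hospital discharge, so that AEs are collected through week 24/month 6, death or withdrawal of consent.
- **Section 11, recording:** enter AEs found at the Section 6 visits on the AE form whatever their expectedness or attribution. Make severity, expectedness and relatedness fields on the form. Keep the serious, unexpected and related filter for expedited reporting only.
- **Section 7.1.4 (Analysis of Secondary Endpoints):** state that these records are the source of the comparison by arm.

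If wider recording is not wanted, the minimum is to correct the window, reconcile Sections 6.4 to 6.8 with Sections 11 to 11.2, and name the records analysed.

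**Cost:** an amendment with IRB approval, site retraining and more form entries. Background AE rates will read higher in both arms. Events collected under the old rule need a flag so that the two periods can be told apart. No procedure is added, because the visits already elicit new signs and symptoms.
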